Delivery of manuscript	01-05-2018

7. Rationale and background

Venous thromboembolism (VTE) in young women is rare, with an annual incidence of approximately 2-5 per 10 000 women (6). An increased risk of VTE associated with oral contraceptive use has long been established and while the absolute risk of VTE in young women is low, the fact that millions of women worldwide are using oral contraceptives indicates that these preparations are responsible for a large number of cases of VTE

(3, 7-11). Several large studies including a review in 2013 by the European Medicines Agency (EMA) concluded that the risk of VTE associated with hormonal contraceptive preparations which contained gestodene, desogestrel, or drospirenone was increased compared with hormonal contraceptive preparations containing levonorgestrel (1, 5, 12, 13).

After the publication of the review by the EMA, the European Commission adopted on 16 2014, a legally binding decision to update the product information of all combined hormonal contraceptives (CHC) throughout the European Union. This included information to patients: awareness of factors that increase the risk of VTE and information to health care professionals: the type of CHC with the lowest VTE risk (levonorgestrel, norethisterone, or norgestimate) and the fact that CHC are contraindicated in the presence of one serious or multiple risk factors for VTE. It is currently unknown whether the publication of this review led to a change in prescription patterns and a subsequent change in the incidence of VTE in young women.

The aim of this study is therefore to investigate the CHC utilisation and prescribing patterns in a sample of Three European Union Member states (Denmark, United Kingdom, and the Netherlands) in a time period including the completion of the 2013 review and implementation of the resulting recommendations and to estimate any changes in the incidence of VTE between the two periods specified.

This study will provide evidence regarding the necessity of the recommendation to use safer oral contraceptive preparations, as it will show whether the implementation of the recommendation was successful and whether it actually affected the incidence of VTE in the target population.

8. Research question and objectives

Was there a change in CHC prescribing patterns between the periods January 2012 – January 2014 and February 2014 – December 2015 and, if so, was there a subsequent change in the incidence rate of VTE?

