1. To investigate trends in new user (initiators) prescribing patterns in the two years preceding the relevant Commission Decision (January 2012 – January 2014) and in a similar period following the decision (February 2014– December 2015).
2. To investigate switching patterns between products among prevalent users including reasons for changes (e.g., reimbursement or regulatory and clinical guidance).
3. Within Objectives 1 and 2, to examine any changes in utilisation in groups defined by patient's clinical and demographic risk factors for VTE as detailed in the warnings and contraindications in the European Union Summary of Product Characteristics (SmPC).
4. To examine any differences in the incidence rates of VTE between the two periods specified and, in light of the results for Objective 1-3, to investigate any measurable association between the observed changes in CHC use and changes in the VTE incidence rates.

9. Research methods

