WP4 The Netherlands. For the calculation of the incidence rate of VTE between the two periods specified, i.e. January 2012 to January 2014 and February 2014 to December 2015, we will analyse new users of CHCs (within each calendar window) and assess whether they will develop VTE within one year of CHC initiation. From the analysis of WP1, we will obtain information on a potential change in the proportion of initiators of each generation of CHC between January 2012- January 2014 and February 2014- December 2015. Since we have information about the prescription patterns among new users, we can assess whether the changes observed in the proportions of each generation is associated with changes in the incidence rate of VTE in women initiating oral contraceptive use. Furthermore, we can study the changes in the incidence of VTE within users of different types (and generations) of oral contraceptives. A change in this incidence over time, may indicate that certain preparations are prescribed to low/high risk individuals. Because we have information about the age and socioeconomic status (risk factors of VTE) of these women, we can stratify analyses on these factors.

WP5 Denmark. Incidence rate of VTE will be estimated from the routinely recorded data based on validated algorithms. VTE will be measured using discharge diagnoses recorded in the Danish National Patient Registry.

WP6 United Kingdom. Incidence rates of VTE will be estimated from the routinely recorded data. VTE will be measured by using diagnoses entered into the electronic primary care records by Read codes. It is a hierarchical classification system, linked to the International Classification of Diseases (ICD 10), but more comprehensive.

WP7 Combining findings from WP1-6 to report on trends in oral contraceptive use in the periods before and after the publication of the 2013 EMA review, i.e., January 2012 – January 2014 and February 2014 – December 2015, and the associated changes in the incidence of VTE in the two periods. These results will be combined in the final report for the EMA and in the manuscript for submission for publication.

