9.2 Data collection and analysis

WP1

Objectives

To obtain the number and proportion of women (within each calendar window) initiating different types of oral contraceptives or per switching pattern using data from the SFK.

Methods

Study population

For the Dutch drug utilization study, we will make use of de-identified data obtained through The SFK, which gathers its data from >95% of community pharmacies in the Netherlands (<https://www.sfk.nl/english>). All women who had one or more prescription of CHC in the period from January 2012 through December 2015 will be included, i.e., both new users as well as prevalent users. Age at initiation and 4 digit postcodes is also available in the SFK database which allows further characterization of CHC users by age and socioeconomic status. The latter information will be retrieved by using information from the Central Bureau of Statistics (CBS), the Netherlands, which keeps record of socioeconomic status by use of 4-digit postcodes. Although SFK does not indicate if women had venous thrombotic disease for which they need to receive anticoagulant treatment, it can be approximated by the first dose of oral anticoagulant (direct oral anticoagulant (DOAC)) or duration of anticoagulant (vitamin K antagonist), which is specific for VTE.

Per calendar year of the study period (1 January 2012 to 31 December 2015), we will identify new users of CHC use. New users will be defined as women between the ages of 18 to 49 years old who do not have a prior prescription of CHC in the two years before.

Furthermore, we will obtain information on prevalent users of CHC and thereby we can assess all individual changes (switches) in CHC in the study period (1 January 2012 to 31 December 2015). Prevalent users of CHC are defined as women who used at least one cycle of oral contraceptives.

Oral contraceptives

We will consider CHCs. According to the EMA review, the CHCs which contain levonorgestrel, norgestimate and norethisterone show the lowest risk of VTE (1). Therefore, additional to the analysis of individual types of combined oral contraceptives, in our analysis, we will group CHC

together according to generation (i.e., the 'second' generation containing levonorgestrel, norgestimate and norethisterone; third generation containing gestodene, desogestrel; and the newer generations containing drospirenone, norelgestromin and cyproterone acetate).

Analysis

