For each calendar year, we provide estimates of the number and proportion of new users of each oral contraceptive type and the number and proportion of switchers (from one type to another or to a different dose) overall and stratified by age at initiation of oral contraceptives (18-24, 25-29, 30-34, 35-39, 40-44 and 45-49 years) and socioeconomic status.

In order to assess the effects of the review on initiation as well as on switching of treatment (between January 2012- January 2014 and between February 2014- December 2015), we will perform segmented regression analysis (16).

For our analysis we will use SPSS for Windows, release 23.0.

WP2

Objectives

To obtain the number and proportion of women (within each calendar window) initiating different types of oral contraceptives or per switching pattern using data from the Danish Civil Registration System and the Danish National Prescription Registry.

Methods

Study population

For the Danish drug utilization study, we will obtain information on use of oral contraceptives from the Danish National Prescription Registry, demographic information (age, sex, vital status and migration) from the Danish Civil Registration System and data on income and education at Statistics Denmark in the study period (1 January 2012 to 31

December 2015). Women with no oral contraceptives prescription prior to study start date (from 2010 onwards) will be followed up until they receive their first oral contraceptive dispensation, become 50 years of age, 31 December 2015, or they emigrate or die. The new users are defined as women with no prior prescription of CHC in the two years before.

To investigate switching patterns among prevalent users, individuals will be defined as prevalent users if they had at least one dispensation for an oral contraceptive between 1 July 2011 and 1 August 2015. Prevalent users will be followed from the date of the study start/entry until switch of treatment (defined as prescription of a new type of CHC before expiration of the days supplied of the previous drug), becoming 50 years of age, December 31st 2015, death or emigration, whichever comes first.

Oral contraceptives

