We will consider each CHC individually and, additional to the analysis of individual types of combined oral contraceptives, in our analysis, we will group CHC together according to generation (i.e., the second generation containing levonorgestrel/norgestimate and ethinylestradiol, the third generation containing gestodene/desogestrel and ethinylestradiol and the newer generations containing drospirenone and ethinylestradiol).

Analysis

For each calendar year, we provide estimates of the proportion of each oral contraceptive type and the number of switchers (from one type to another or to a different pill strength) overall and stratified by age at initiation of CHC (18-24, 25-29, 30-34, 35-39, 40-44 and 45-49 years).

We will estimate incidence rates of initiating CHC use per 1000 person years at risk including 95% confidence intervals for each calendar year using incident dispensation as the indicator of CHC initiation. Similarly, we will provide estimates of incidence rates of switching per 1000 person years at risk including 95% confidence intervals for each calendar year of the study period.

In order to assess the effects of the review on initiation as well as on switching of treatment (between January 2012- January 2014 and between February 2014- December 2015), we will perform segmented regression analysis, taking the two time periods into account.

For our analyses we will be using SAS version 9.2 or higher.

WP3

Objectives

To obtain the number and proportion of women initiating different types of oral contraceptives in UK between January 2012 to December 2015 and to investigate switching pattern using data from The Health Improvement Network (THIN) primary care database.

Methods

Study population

For the UK drug utilization study, we will make use of anonymised primary care data from when women consult their general practice to obtain oral contraceptives. For each calendar year of the study period (1 January 2012 to 31 December 2015) we will identify women who were between 18 and 49 years and have been registered for at least two years prior with one of the general practices that contributed data to THIN. Individuals with no oral contraceptives prescription prior to study entry (from 2010 onwards) will be followed up until they receive their first oral contraceptive prescription, they become 50 years of age, 31 December 2015, or leave the practice. The new users are defined as women with no prior prescription of CHC in the two years before.

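### Objective 3 promises CHC use by SmPC clinical risk factors and contraindications, but WP1 to WP3 fix no clinical stratum in the Netherlands or Denmark, only BMI and smoking in the UK, and no contraindication group anywhere

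*Protocol*

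**What the plan says.** Objective 3 (Protocol section 8, also in the PASS information table and the abstract) applies to both initiation and switching. It defines the groups of interest by "clinical and demographic risk factors for VTE as detailed in the warnings and contraindications" in the SmPC. Section 7 gives the background: besides naming the lowest-risk products, the updated product information told health professionals that "CHC are contraindicated in the presence of one serious or multiple risk factors for VTE".

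Section 9.2 then sets the strata for each utilisation work package:

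- **WP1, Netherlands.** Results are "stratified by age at initiation of oral contraceptives (18-24, 25-29, 30-34, 35-39, 40-44 and 45-49 years) and socioeconomic status". The patient characteristics described are equally short: "Age at initiation and 4 digit postcodes is also available in the SFK database", with the postcode used to derive socioeconomic status.
- **WP2, Denmark.** Results are "overall and stratified by age at initiation of CHC (18-24, 25-29, 30-34, 35-39, 40-44 and 45-49 years", and the list stops there. Income and education are obtained from Statistics Denmark but are not named as strata.
- **WP3, United Kingdom.** The same age bands, plus deprivation quintiles, BMI and smoking.

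Diagnoses enter only in the VTE work packages. For WP5, section 9.1 states that "VTE will be measured using discharge diagnoses recorded in the Danish National Patient Registry". WP6 uses Read codes. Both restrict their cohorts to women without a VTE record from 2002 onwards. Section 9.5 discusses unconfirmed and fatal VTE and says nothing about Objective 3.

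**The concern.** An objective that names its subgroups should have an analysis that forms them. Here the objective points to clinical risk factors and contraindications, while the strata are mostly demographic or social. If the plan is followed as written, the report can show how product choice changed by age. It cannot show whether fewer women with a contraindication, or with several risk factors, were started on or switched between CHCs after the decision.

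The gap carries forward, because Objective 4 is to be interpreted in light of Objectives 1 to 3. What remains on clinical selection is indirect: WP4 and WP6 say that a change over time in VTE incidence within a product may point to selective prescribing to lower- or higher-risk women. That is a statement about outcome rates. A direct description of who was prescribed what is the purpose of Objective 3.

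**Working it through.** No arithmetic beyond counting applies. The check sets the objective against the strata that section 9.2 fixes for initiation and switching.

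| Work package | Demographic or social strata | Clinical strata | Contraindication or multiple-risk-factor group |
|---|---|---|---|
| WP1 Netherlands | 2 (age, area socioeconomic status) | 0 | 0 |
| WP2 Denmark | 1 (age) | 0 | 0 |
| WP3 United Kingdom | 2 (age, deprivation) | 2 (BMI, smoking) | 0 |

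Clinical strata therefore exist in 1 of 3 countries, and contraindication or multiple-risk-factor groups in 0 of 3.

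**Does another part of the protocol fill the gap?**

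- The abstract lists age, socioeconomic status, BMI and smoking as risk factors for stratifying VTE incidence in Denmark and the UK, and marks the last two as UK only. This concerns incidence, and it adds no new clinical factor.
- WP4 stratifies by age and socioeconomic status, WP5 by age at initiation, and WP6 by age, deprivation, BMI and smoking. None defines a contraindication group.
- Prior VTE appears in WP5 and WP6 only as a cohort restriction. It is not a utilisation subgroup.
- The ENCePP checklist adds no clinical stratum.

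**Which of the missing pieces could be built from the sources named?**

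- *Prior VTE, Denmark and UK:* yes. WP5 and WP6 must already search for it from 2002. WP2, however, names only the Civil Registration System, the Prescription Registry and Statistics Denmark. The Patient Registry is named for WP5, so its linkage has to be extended.
- *Multiple risk factors, UK:* feasible from age, BMI, smoking and Read-coded diagnoses, once the list is written down.
- *Multiple risk factors, Denmark:* not shown to be feasible. BMI and smoking are UK only, and no diagnoses other than VTE are described.
- *Netherlands:* SFK holds dispensings. Anticoagulant dispensing is the planned VTE proxy after initiation, and for vitamin K antagonists it depends on treatment duration. The protocol does not address its use as a history marker before initiation.

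**The case against.** The best defence is that subgroup definitions and code lists commonly sit in the statistical analysis plan, which is not at hand. That is fair for code lists. It does not cover this gap, because the protocol itself fixes both the strata and the data sources by work package, and the sources named for WP2 are not described as holding diagnoses. Adding one is a protocol decision.

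A second defence is that sections 7 and 9.2 (WP7) describe the evaluated recommendation as the use of safer preparations, so product choice is the main question and contraindicated use enters only through Objective 3. That stands and limits the consequence, but Objective 3 is still a stated objective.

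Several stronger readings are tempting, and the documents do not support them:

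- *Most of the objective goes unanswered.* The SmPC list is not reproduced, so no fraction can be counted. Age is covered in all three countries.
- *Half of the regulatory message is left untested.* Section 7 lists several messages without weighting them.
- *The channelling inference in WP4 and WP6 cannot be separated from age mix or noise.* Age stratification is planned for the Netherlands and the UK, 95% confidence intervals are planned, and the protocol claims only that a change may indicate selection.
- *All the data needed are already held.* On the documents this is supported only for prior VTE in Denmark and the UK, and for the UK variables listed.

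**Conclusion.** The mismatch is real and should be corrected. The clinical part of Objective 3 is absent in the Netherlands and Denmark and limited to BMI and smoking in the UK. The contraindication and multiple-risk-factor part is absent in all three countries, and section 9.5 does not disclose this. The demographic part is answered through age everywhere, so a reader should not conclude that the objective fails as a whole.

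The count rests only on the protocol text. The remedy rests on one assumption: that prior VTE is among the serious risk factors in the SmPC, since section 7 refers to such factors without listing them. The documents give no prevalence for any flagged group, so the precision of the added results cannot be stated.

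**What to change.** 1. **WP2 and WP3:** add a prior-VTE flag dated before the initiating or switching prescription, using the lookback from 2002 already planned in WP5 and WP6.
2. **WP3:** add a multiple-risk-factor group built from recorded age, BMI, smoking and Read-coded diagnoses. State in the protocol which SmPC factors count.
3. **WP2:** name income and education as strata, since they are already obtained.
4. **WP2 and WP3 reporting:** give the flagged proportion of initiators and of switchers by window, within the planned segmented regression.
5. **WP1:** use prior anticoagulant dispensing as an exploratory proxy only, labelled as such.
6. **Objective 3 and section 9.5:** where a database cannot measure a factor, narrow the objective for that country and state the limit. If the sponsor prefers not to add flags, this is the minimum repair.

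Cost: the Danish Patient Registry linkage must be extended to WP2, and code lists and the SmPC factor list must be written. Flagged cells will be small, so these results would be mainly descriptive. Item 6 alone costs only a text change, but leaves the clinical question unanswered.

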9.1 Study design

Drug utilisation study and epidemiological cohort study using data retrieved from electronic health records from three EU member states, i.e., the Netherlands, Denmark, and the United Kingdom. The study will comprise of seven work packages (WP).

WP1 The Netherlands. Drug utilisation study into prescribing patterns including new use as well as switching between products in the periods before and after implementation of the decision of the European Commission, i.e. January 2012 to January 2014 and February 2014 to December 2015 by using de-identified data obtained through The Dutch Foundation for Pharmaceutical Statistics (SFK), which gathers its data from >95% of community pharmacies in the Netherlands (<https://www.sfk.nl/english>). The drug utilization study described in this WP is descriptive in nature. The outcome will be the number and proportion of women (within each calendar window) initiating different types of oral contraceptives or per switching pattern.

WP2 Denmark. Drug utilisation study into prescribing patterns including new use as well as switching between products in the periods before and after implementation of the decision of the European Commission, i.e. January 2012 to January 2014 and February 2014 to December 2015 by linking data from the following databases: The Danish Civil Registration System (14) (personal identifier, migrations, vital status); and the Danish National Prescription Registry (15) (outpatient dispensations, including date, ATC code, defined daily dose, amount dispensed).

WP3 United Kingdom. Drug utilisation study into prescribing patterns including new use as well as switching between products in the periods before and after implementation of the decision of the European Commission, i.e. January 2012 to January 2014 and February 2014 to December 2015 by using anonymised prescribing data from UK primary care which can be linked to the British National formulary and also to ATC codes.

WP4 The Netherlands. For the calculation of the incidence rate of VTE between the two periods specified, i.e. January 2012 to January 2014 and February 2014 to December 2015, we will analyse new users of CHCs (within each calendar window) and assess whether they will develop VTE within one year of CHC initiation. From the analysis of WP1, we will obtain information on a potential change in the proportion of initiators of each generation of CHC between January 2012- January 2014 and February 2014- December 2015. Since we have information about the prescription patterns among new users, we can assess whether the changes observed in the proportions of each generation is associated with changes in the incidence rate of VTE in women initiating oral contraceptive use. Furthermore, we can study the changes in the incidence of VTE within users of different types (and generations) of oral contraceptives. A change in this incidence over time, may indicate that certain preparations are prescribed to low/high risk individuals. Because we have information about the age and socioeconomic status (risk factors of VTE) of these women, we can stratify analyses on these factors.

WP5 Denmark. Incidence rate of VTE will be estimated from the routinely recorded data based on validated algorithms. VTE will be measured using discharge diagnoses recorded in the Danish National Patient Registry.

WP6 United Kingdom. Incidence rates of VTE will be estimated from the routinely recorded data. VTE will be measured by using diagnoses entered into the electronic primary care records by Read codes. It is a hierarchical classification system, linked to the International Classification of Diseases (ICD 10), but more comprehensive.

WP7 Combining findings from WP1-6 to report on trends in oral contraceptive use in the periods before and after the publication of the 2013 EMA review, i.e., January 2012 – January 2014 and February 2014 – December 2015, and the associated changes in the incidence of VTE in the two periods. These results will be combined in the final report for the EMA and in the manuscript for submission for publication.

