For the UK drug utilization and cohort study, we will make use of anonymised primary care data. In the period January 2012- December 2015, women between the ages 18-49 years who have been registered for at least two years prior with one of the general practices that contributed data to The Health Improvement Network (THIN) primary care database will be included. New and prevalent users will be identified. In addition, information is available on social deprivation, body mass index (BMI) and smoking status which can be used to stratify patients on the risk of VTE.

Study size:

In 2014, approximately 1.4 million women between 15-50 years used oral contraceptives in the Netherlands, of whom ~1.3 million are registered in the SFK. In women between 15-25 years, the majority of oral contraceptive users will be starters (the new users in our study will include these starters as well as women who have used CHC in the past, but not in the previous two years). Data from the CBS indicated, that in 2014, there were 1 011 127 women between 15-25 years, of whom ~59% were using oral contraceptives (n=596 565). From unpublished data from the department of Clinical Epidemiology, Leiden University, we estimate that in 2-year period, approximately 16% of premenopausal women switch from one oral contraceptive agent to another. With 1.3 million oral contraceptive users, this indicates ~212 000 switches per 2-year period.

As mentioned above, the number of women between 15-25 years using CHCs in 2014 is 596 565. This number will vary in the other years of the study period. From literature it is known that the risk of VTE is increased 8-fold among starters in the first year of use (in the first three months, the risk is increased 13x) (3). However, this risk differs for the different types of CHCs. Also the proportion of each generation of CHC will differ in each observation window. Therefore, it is difficult to estimate the number of cases of VTE in new users of CHC in the study period January 2012- December 2015.

In Denmark, annually more than 330 000 women receive CHC (<https://laegemiddelstyrelsen.dk/da/udgivelser/2016/~-/media/CD29697BD25C4642968D9386979472A9.ashx>; <http://medstat.dk/>). The annual incidence rate of VTE is about 4 per 10 000 for women of reproductive age not using oral contraceptives. Thus, a conservative estimate for 4 years of follow-up assuming the size of the study population of 300 000, is at least 480 cases of

VTE (4).

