A previous UK primary care database study estimated the crude incidence rate of VTE cases per 10 000 women years was 5.9 (95% confidence interval 5.7-6.0) in CPRD and 6.1 (6.0- 6.3) in QResearch (5). In UK around 28% use oral contraceptives and CHC form a substantial proportion of these.

Data analysis:

In order to assess the effects of the review on initiation (new use) as well as on switching of treatment (between January 2012- January 2014 and between February 2014- December 2015), we will perform segmented regression analyses.

For the Dutch part of study, we will calculate the incidence of VTE among the new users of CHC within each calendar window (January 2012- January 2014 and February 2014- December 2015). From segmented regression analysis, we will obtain information on a potential change in the proportion of different types of oral contraceptives in new users separately and grouped according to generation of CHC after the European commission decision (January 2014). Since we have information about the prescription patterns among new users, we can assess whether the changes observed in the proportions of use of each generation is associated with changes in the incidence rate of VTE in women initiating oral contraceptive use. Furthermore, we will study the changes in the incidence of VTE within users of different types (and generations) of CHCs. A change in this incidence over time, may indicate that certain preparations are prescribed to low/high risk individuals. We will stratify analyses on age and socioeconomic status (risk factors of VTE) of the women.

For the Danish and UK part of the study, estimates on the incidence of VTE will be calculated. Overall estimates as well as estimates stratified by risk factors such as age, socio-economic status, BMI (UK only), smoking status (UK only) will be provided. For the Danish and UK data we will compare the age-standardised incidence rates of VTE against the age standardised initiations of oral contraceptives in order to evaluate whether overall changes in CHC use is associated with overall changes in incidence of VTE.

Milestones:

Task	Month
Data extraction and analysis	10
Writing study results for the EMA	3
Writing manuscript for submission to peer-reviewed journal	3

5. Amendments and updates

None

6. Milestones

Milestone	Planned date
Start of data collection (extraction)	31-03-2017
End of data collection (extraction)	31-12-2017
Final report of study results	01-05-2018

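### The only output named for the Dutch segmented regression is the product share among CHC initiators; type-specific initiation rates over the female population should be modelled beside it

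*Protocol*

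**What the plan says.** Section 9.1 (WP1) sets the Dutch outcome: "The outcome will be the number and proportion of women (within each calendar window) initiating different types of oral contraceptives or per switching pattern". The Dutch source population in section 9.2 (WP1) is defined by exposure: "All women who had one or more prescription of CHC in the period from January 2012 through December 2015 will be included". Women without a CHC prescription are not in it.

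For each calendar year, WP1 promises that "we provide estimates of the number and proportion of new users of each oral contraceptive type and the number and proportion of switchers" will be given, overall and by age band and socioeconomic status. No Dutch rate of initiation appears anywhere in the protocol.

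The WP1 analysis text gives the purpose of the segmented regression ("In order to assess the effects of the review on initiation as well as on switching of treatment") but names no dependent variable. The abstract (Data analysis) says what the Dutch regression will yield: "a potential change in the proportion of different types of oral contraceptives in new users separately and grouped according to generation of CHC". WP4, in sections 9.1 and 9.2, describes the same output as the proportion of initiators by generation and relates it to VTE incidence in initiators.

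Denmark is handled differently in section 9.2 (WP2): "We will estimate incidence rates of initiating CHC use per 1000 person years at risk". WP3 plans the same kind of rate for the UK. The abstract also plans to compare VTE rates with age-standardised initiations, but for Denmark and the UK only.

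**The concern.** Section 7 describes two messages in the Commission Decision. One tells prescribers which CHCs carry the lowest VTE risk. The other says that CHCs are contraindicated with one serious or several risk factors. The first acts on the choice of product, the second on whether a woman starts at all. A share among starters measures the first and is blind to much of the second.

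The study undertakes to show whether the recommendation was implemented successfully. The Dutch data are a large part of that evidence: about 1.3 million users, against more than 330 000 CHC recipients a year in Denmark (the size of the UK source is not given). If the modelled Dutch result is a share only, a real fall in initiation could be reported as no effect, and a fall in higher-risk starts could be reported as uptake of lower-risk products.

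**Working it through.** **Inputs from the protocol.** Windows: January 2012 to January 2014 is 25 months, and February 2014 to December 2015 is 23. Risk per 10 000 women a year (table in the abstract): 5-7 for levonorgestrel, norethisterone or norgestimate; 9-12 for drospirenone, gestodene or desogestrel.

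**Assumptions, not in the protocol.** 10 000 initiations a month; lower-risk share before the Decision 60% (range 50-80%); 3.5 million women as a constant denominator; changes of 20% or 30%, immediate and without noise.

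**The plan's own figure.** The protocol gives no figure for the segmented regression. The CBS-based study-size figure reproduces: 1 011 127 × 0.59 = 596 565 users.

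**Share formulas.** Let L and H be lower- and higher-risk starts, with share s = L/(L+H).

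- All starts fall by a fraction f: (1−f)L / [(1−f)(L+H)] = s, so no change. Example with 10%: 54/(54+36) = 60.0%.
- Only higher-risk starts fall, by d: L / [L+(1−d)H]. Example with 40 falling to 30: 60/(60+30) = 66.7%.
- A fraction d of higher-risk starts moves to lower-risk products: (L+dH)/(L+H).

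**Segmented regression** (intercept, trend, step, change in trend; 25 months before, 23 after) at a 60% starting share:

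| Scenario | Step in lower-risk share | Step in lower-risk starts per 1000 women a month | Step in higher-risk starts per 1000 women a month |
|---|---|---|---|
| All starts −20% | 0.0 points | −1200/3.5 million = −0.343 | −800/3.5 million = −0.229 |
| Higher-risk starts −30%, lower-risk unchanged | 60/88 = 68.2%, +8.2 points | 0.000 | −1200/3.5 million = −0.343 |
| 30% of higher-risk starts substituted | 72/100 = 72.0%, +12.0 points | +1200/3.5 million = +0.343 | −0.343 |

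At starting shares of 50, 60, 70 and 80%, the second scenario gives +8.8, +8.2, +6.9 and +5.1 points, and the third gives +15.0, +12.0, +9.0 and +6.0. The sign is always the same, and size does not separate them either. At a 60% starting share, a rise of 8.2 points also results from substituting 8.2/40, or about 20%, of higher-risk starts, with no fall in total starts. The type-specific rates separate all three scenarios.

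**Counts.** If totals are compared by window, constant monthly initiation gives 23/25 = 0.92, an apparent fall of 8%. Calendar-year counts avoid this, but they still lack a denominator, and calendar year 2014 includes January, which belongs to the earlier window.

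**VTE per initiator (WP4).** With midpoints 6 and 10.5 per 10 000, the mix gives 0.6×6 + 0.4×10.5 = 7.8. A proportional fall in starts leaves this at 7.8, so in that case the second Dutch measure is flat as well.

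**The case against.** The strongest reply is that WP1 reports numbers as well as proportions, by type, year, age and socioeconomic status. In the 60/40 example the count table would show 60 and 30, and after a uniform 10% fall it would show 54 and 36. This stands. A reader might infer that the Dutch data cannot tell a fall in initiation from substitution; the documents do not support that. The limit applies to the share regression alone.

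Secondly, the WP1 analysis text names no dependent variable. An assessment of effects on initiation could include counts, and such detail may be left to an analysis plan. This also stands in part: the protocol does not confine the regression to shares. But a share is the only output it names, in the abstract and twice in WP4.

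Thirdly, the wording is not peculiarly Dutch. WP6 describes the UK regression output in the same share terms, and neither WP2 nor WP3 says that the regression is run on the person-year rates. Denmark reports proportions by type, and UK shares can be derived from the numbers of initiators. So a reader who infers that the Dutch results cannot be set beside the other two in WP7 goes too far: shares are available in all three. What the Netherlands lacks is the rate.

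Fourthly, the product mix is the fitting exposure for WP4, where VTE incidence is also per initiator. That is a reason to keep the shares, not to rely on them alone.

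Finally, a trend term absorbs smooth population drift, and nothing in the protocol shows that the Dutch female population shifted enough in four years to distort counts. This is fair. The denominator's main gains are age standardisation and approximate comparability with the other countries; most of the separation between scenarios comes from modelling counts by type.

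**Conclusion.** The point holds as a limit of the named regression output. A segmented regression on shares among initiators returns zero for a fall in starts that is exactly proportional across types. It also cannot separate fewer higher-risk starts (+5.1 to +8.8 points for a 30% fall) from substitution (+6.0 to +15.0 points for 30% substituted) over assumed starting shares of 50-80%. These sizes rest on the assumed changes and shares; the algebra does not. The planned counts partly fill the gap, but descriptively, without a denominator and, by window, over unequal lengths. This is a worthwhile and cheap improvement to the Dutch analysis, not a defect that makes the Dutch data uninformative.

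**What to change.** In WP1, name the dependent variable and run the segmented regression also on initiation counts by type and by generation, for example monthly, with the CBS female population aged 18-49 by age band as offset. Report age-standardised initiations per 1000 women. Keep the shares as the product-mix measure for WP4, and interpret a change in share only together with the type-specific rates. Stratify the rates by postcode-based socioeconomic group only if CBS denominators exist at that level; the protocol does not show that they do.

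The cost is a paragraph of analysis text and a CBS population table. The protocol already draws on such counts ("Data from the CBS indicated, that in 2014, there were 1 011 127 women between 15-25 years"), although for another age range, and no new patient data are needed. The downside is that the denominator is all women, not women off CHC, so the Dutch rates are only approximately comparable with the person-year rates of WP2 and WP3; WP7 should say so. For the UK, the share wording in WP6 can be extended to the rates already planned in WP3.
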